2.4.3 Strengths and limitations

Strengths of our study include a randomized control design, as well as a large cohort of patients who will be eligible for enrollment. CUIMC has 9 obstetric clinics which annually experience 27,612 deliveries, of which 2,853 (approximately 160/month) are affected by HDP. An additional strength of our study is that the Philips RPM system has been previously tested in pilot studies at other institutions and is currently being trialed in a 30-day pilot program in the Emergency Department at CUIMC, projected to end in mid-October 2018, prior to the projected start of this study. If there are any unforeseen issues with equipment or installment, these will be able to be resolved prior to the rollout of our study.

Project limitations include potential fear among patients of a new technology that could limit enrollment. Additionally, patients may not present to their 7-10 day postpartum blood pressure check, which would limit the results; however, we did try to account for this when calculating our sample size. Finally, a limitation of the study is that control patients may be more cognizant of checking their blood pressures due to being enrolled in a research protocol, and this may falsely inflate their blood pressure recording rates. However, even if the control group has higher compliance with blood pressure measurements than the baseline population, we still anticipate that the study group will have a statistically significant increase in these measurements.

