2. Arrangements for a nursing service to visit the patient’s home for a blood pressure check within the first few days after discharge. *The exact timing of this is not standardized; for example, if the patient is discharged on Friday, the nurse may come 72 hours later on Monday; if the patient is discharged on Thursday, the nurse may come 24 hours later on Friday.*
3. An appointment for a blood pressure check in the clinic where the patient received prenatal care at 7-10 days postpartum; the patient is instructed to bring logs of their twice daily blood pressure measurements to this visit. *Patients with private insurance are told to make this appointment with their prenatal care provider but are not given the*

appointment prior to discharge. Patients who are discharged on or after 7 days postpartum are told to follow up in one week

4. *An appointment for a 6-week postpartum visit. Patients with private insurance are told to make this appointment with their prenatal care provider but are not given the appointment prior to discharge.*

If followed in full by the patient, these policies do follow the current guidelines set forth by ACOG. However, extrapolating from the limited published data regarding follow-up rates and from approximations from our own publicly-insured population, it is reasonable to presume that only about half of these patients present for their one-week blood pressure check appointment.¹⁵ Poor follow-up is not a problem unique to our institution. In a secondary analysis of factors associated with postpartum follow-up and persistent hypertension in women with severe preeclampsia by Levine et al, the 6-week follow-up rate was 52%. Among those with 6-week follow-up, 21% had persistent hypertension.⁴ With low-follow up rates and high rates of persistent hypertension in those that do follow up, clearly there is a large subset of women with continued hypertension who are simply lost to care. Barriers to care in the postpartum period include lack of a consistent provider, lack of understanding of discharge instructions whether due to poor health literacy, a language difference or a failure of the provider to properly explain instructions, and difficulties with transportation. Additionally, many women have difficulty managing their own health issues when also taking care of a newborn, possibly with limited support.¹⁶

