2.4 Statistical Analyses

2.4.1 Sample size and statistical power

Though data on the rate of follow up in patients with HDP are scarce, we will presume that the percentage of patients who record their blood pressures accurately postpartum is similar to the rate noted in the few studies that have measured similar metrics, approximately 43.7%.¹⁵ We currently have IRB approval for a retrospective study to assess the postpartum follow up of women with HDP over the past 2 years at CUIMC (protocol AAAR9887). Until data collection for this study is complete, we will not precisely know the baseline rate of compliance with blood pressure measurements in the first 7-10 days postpartum. Therefore, in order to err on the side of making sure we are well powered, we will use 60% as an estimated percentage of twice daily blood pressures that are recorded in the usual care group. Aiming to achieve a rate of 80% for twice daily blood pressure recordings in the study group with 80% power, we would need to recruit 81 patients to each group. Allowing for the possibility of loss to follow-up and to compensate for the reduced power due to statistical adjustment for potential confounders, we inflated the sample size by 25%. 101 patients will therefore need to be recruited to each group, or 202 patients total. The randomization sequence was built based on an overestimate of dropout rate. Therefore, we increased our target enrollment from 202 to 220. Once the sample size is reached, enrollment will stop.

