2.4.2 Statistical analysis

For analysis of discrete (categorical) data in independent samples, the Chi-squared test or Fisher exact probability test will be utilized. For group comparisons, continuous data that satisfy the assumptions of normality and homoscedasticity (homogeneity of variance) will be analyzed by t-test (for 2 independent samples) or analysis of variance (>2 groups, ANOVA) with post hoc comparisons by Scheffe tests. When possible, continuous data that do not fulfill the aforementioned assumptions will be mathematically transformed (e.g., logarithmic transformation) before performing t-tests or ANOVA. In some cases, data that do not satisfy these assumptions will be analyzed by nonparametric methods [Mann-Whitney U Test (for two independent samples) or Kruskal-Wallis One-Way ANOVA (for more than two independent

samples)]. Significant Kruskal-Wallis ANOVAs will be followed by Dunn tests for post hoc analysis. The degree of linear association between variables will be measured by the Pearson product moment correlation coefficient or the Spearman rank-order correlation coefficient and their corresponding tests of significance. Multivariate linear or logistic regression will be utilized where appropriate. In all cases, statistical significance will be assumed when $p < 0.05$. Propensity score analysis will be used as a balancing score as deemed necessary.

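### The sample size allows for 20–26% loss, but the plan presumes about half of usual-care women miss the visit where control logs are collected; with control-only loss, power is about 74–77%, not 80%

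*Combined protocol and SAP*

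**What the plan says.** Section 2.4.1 sizes the trial as a comparison of two proportions. For controls, "we will use 60% as an estimated percentage of twice daily blood pressures that are recorded in the usual care group". For the monitored arm: "Aiming to achieve a rate of 80% for twice daily blood pressure recordings in the study group with 80% power". The result is that "we would need to recruit 81 patients to each group".

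To cover both loss to follow-up and the power cost of adjusting for confounders, "we inflated the sample size by 25" per cent, giving 101 per group and 202 in total. Later "we increased our target enrollment from 202 to 220". That rise is attributed to an overestimated dropout rate in the randomization sequence, and the rate is not given.

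Section 2.4.3 lists a missed 7-10 day check as a limitation and adds "we did try to account for this when calculating our sample size".

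On attendance under usual care, section 2.1 says "it is reasonable to presume that only about half of these patients present for their one-week blood pressure check appointment". Section 2.3.1 asks controls to bring their logs to that visit and takes the counts of readings for each group there. Section 2.3.6 ends the primary outcome window at the same assessment. Sections 2.3.1 and 2.3.7 say that the monitored arm's readings are transmitted to and stored in the eCC software.

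**The concern.** The reassurance in 2.4.3 rests on an allowance that was not built from the plan's own attendance figure. The inflation absorbs a loss of about one in five, and part of it is already committed to covariate adjustment. The only attendance figure for this visit implies that about one usual-care woman in two does not come. Section 2.4.1 neither mentions that figure nor states a loss rate for either arm.

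The stated 80% power is at stake. If control women who miss the visit contribute no primary outcome, the comparison has fewer evaluable controls than the calculation needs, and a reader relying on 2.4.3 would not know it.

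**Working it through.** **Inputs.** Control rate 60%, monitored rate 80%, power 80%, 81 per arm, 25% inflation, 101 per arm, target 220 (all 2.4.1). The target is 110 per arm if allocation is 1:1, which is assumed. Significance level 0.05 (2.4.2: "In all cases, statistical significance will be assumed when" p < 0.05); two-sided is assumed because sidedness is not stated. Usual-care attendance about 50% (2.1).

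**Reproducing the plan's figure.** With pooled variance and no continuity correction:

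n = [1.96·√(2·0.7·0.3) + 0.8416·√(0.24 + 0.16)]² / 0.20² = 81.2 per arm.

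This agrees with the stated 81 (82 if rounded up; the arcsine formula gives 80.3, so 81). Then 81 × 1.25 = 101.25, hence 101 per arm and 202 in total.

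**Loss tolerated while keeping 81 evaluable in each arm.**
- At 101 per arm: 1 − 81/101 = 19.8%.
- At 110 per arm: 1 − 81/110 = 26.4%.

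Both assume equal loss and that none of the allowance is spent on covariate adjustment.

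**Power after loss.** Power = Φ[(|p₁ − p₂| − 1.96·SE₀)/SE₁], with p̄ = (n₁p₁ + n₂p₂)/(n₁ + n₂), SE₀ = √[p̄(1 − p̄)(1/n₁ + 1/n₂)] and SE₁ = √[p₁(1 − p₁)/n₁ + p₂(1 − p₂)/n₂].

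For 55 controls versus 110 monitored women: p̄ = (55·0.6 + 110·0.8)/165 = 0.733, SE₀ = 0.0730, SE₁ = 0.0763. Power = Φ[(0.20 − 0.1431)/0.0763] = Φ(0.745) = 77.2%.

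| Evaluable, control v monitored | Situation | Power |
|---|---|---|
| 81 v 81 | the plan's base case | 79.9% |
| 101 v 101 | no loss at 202 | 87.9% |
| 110 v 110 | no loss at 220 | 90.5% |
| 50.5 v 101 | half of controls lost, at 202 | 73.8% |
| 55 v 110 | half of controls lost, at 220 | 77.2% |
| 62 v 110 | 56% of controls evaluable, at 220 | 80.0% |
| 66 v 110 | 60% of controls evaluable, at 220 | 81.4% |
| 50.5 v 50.5 | half lost in both arms, at 202 | 59.4% |
| 55 v 55 | half lost in both arms, at 220 | 63.2% |

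**Sensitivity to the control rate.** With 43.7%, the literature figure in 2.4.1, instead of 60%, power is 97% at 50.5 v 50.5 and 98% at 55 v 55. It is higher still with control-only loss.

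**Sensitivity to the outcome scale.** If the outcome is analysed as a per-woman percentage with a 20-point difference, power = Φ[20/(SD·√(1/n₁ + 1/n₂)) − 1.96]. The plan gives no SD, so these values are assumptions. For 55 v 110, power is 93% at SD 35, 86% at SD 40 and 77% at SD 45. The SD 40 case is 20/(40·0.1651) − 1.96 = 1.07, and Φ(1.07) = 86%.

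**The case against.** The case on the other side is substantial, and most of it stands as a limit on the size of the problem.

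- **The half is not a forecast for randomised women.** Section 2.1 extrapolates it from limited published data and from approximations in the site's publicly insured patients. Section 2.3.1 gives both groups an appointment, whereas under usual care privately insured women are left to make their own. Section 2.4.3 expects enrolment itself to improve recording among controls. Attendance in the trial could well exceed 50%.
- **Monitored-arm data do not depend on the visit.** A reader might infer that half of both arms is lost and that the trial has only 63% power. The documents do not support that as the main case, because the monitored arm's readings are stored electronically. The 63% figure (55 v 55) is a lower bound at half control attendance, and it requires the monitored data to be lost as well.
- **Needing 81 evaluable in each arm holds only for equal loss.** With all 110 monitored women evaluable, about 62 controls are enough.
- **The 60% control rate was chosen to be cautious.** At 43.7% there is no shortfall.
- **The plan never says that non-attenders are excluded.** Section 2.3.7 asks controls for a record without tying it to the visit, and follow-up runs to the postpartum visit, so logs could be obtained later.
- **The wording in 2.4.3 is modest.** It reports an attempt, within a paragraph that admits the results would be limited.

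What survives is narrower. The 81, the 101 and the 80% all rest on 60% versus 80%, so that is the calculation on which the power claim must be judged. The plan gives no rule for obtaining or scoring a non-attending control's readings, and it shows no link between the 25% and the attendance it presumes.

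**Conclusion.** The concern holds in a limited form. The stated allowance tolerates 20% equal loss at 101 per arm and 26% at 110, against about 50% presumed non-attendance in usual care. The documents therefore do not show that non-attendance was accounted for.

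In the best-supported case, with loss confined to controls, half of them attending and non-attenders not evaluable, power is about 74% to 77%. That is 3 to 6 points below the stated 80%. This rests on two-sided 5% testing, 1:1 allocation, the 60% and 80% design rates, and binary scoring of the outcome.

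The conclusion that the trial is underpowered does not follow. The shortfall disappears at about 56% control attendance with 110 per arm, or at the 43.7% control rate. On a per-woman percentage scale, 55 v 110 keeps 80% at an assumed SD of 35 or 40 but not at 45. What the plan lacks is a stated loss assumption that supports its power figure.

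**What to change.** In 2.4.1, state the loss assumed in each arm and restate power for control-only loss: about 74% at 101 per arm and 77% at 110 per arm if half of controls are evaluable. Add what 80% requires on the plan's own calculation: about 62 evaluable controls if all 110 monitored women are evaluable, or 81 per arm if loss is equal.

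In 2.4.3, replace the remark that non-attendance was considered with the equal loss actually tolerated, 20% at 101 and 26% at 110 per arm, noting that the same allowance also covers covariate adjustment.

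The change is a few sentences in two sections. No additional recruitment is proposed. The cost is a slightly less favourable stated power.

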2.5. Anticipated outcomes

The primary outcome will be the difference in the percentage of twice-daily blood pressures reported between hospital discharge and the outpatient blood pressure assessment. We anticipate that the patients enrolled to RPM will have a significantly higher percentage of blood pressures recorded. Thus, there will be more data, available at an earlier time point in the postpartum period, which providers can use to make decisions regarding titrating medications and need for closer monitoring. We anticipate that patients enrolled in RPM will have more communication with their obstetric providers, higher compliance with their scheduled postpartum visits, and better blood pressure control at 6 weeks postpartum. We also anticipate that these patients will feel like they have had a more active role in their own care, and will feel more connected to their providers during the fragile and currently under-monitored postpartum period.

2.6. Significance

There are several knowledge gaps in the postpartum management of women with HDP. The short term postpartum course of BP in women with HDP and time to normalization of BP in women with HDP have not been well described. Clinical characteristics associated with the

duration of postpartum HTN and the adherence to and tolerability of RPM in the postpartum state are unknown. These knowledge gaps have important clinical implications and answering them will provide valuable information regarding the feasibility of out-of-office BP monitoring in order to care for women with HDP, who have been shown to have extremely low rates of follow-up and adherence to care. The overall goal of this project is to collect empiric data for future guidelines on the optimal use of RPM among postpartum women with HDP.

2.7 Timeline

Enrollment is planned to begin in early November of 2018, as soon as IRB approval is granted and the pilot program is complete in the Emergency Department (currently ongoing and projected to end mid-October 2018). This pilot program aims to trial the use of the Philips RPM system with Emergency Department patients, to ensure feasibility of use. We plan to recruit patients from the postpartum service after delivery. The sample size required is 101 patients per group. We anticipate that these patients will be successfully recruited into the study within a 6-month period, ending approximately in April to May of 2019. These patients will need to be followed until 6 weeks postpartum. We anticipate that the study will be completed by July 2019.

2.8. Environment

The Columbia Department of OB/GYN brings substantial experience and skill in organizing and participating in clinical research. We have a strong track record in all areas of collaborative research including protocol design, implementation, data analysis and dissemination of findings. Our productivity is facilitated by a number of factors: (1) A critical mass of academic full time faculty with sufficient time and skill to perform clinical research, (2) the presence of a diverse patient population willing to participate in research initiatives, and (3) an established research environment in which clinicians accept participation in research initiatives as a major role of a teaching institution. This has led to a longstanding reputation for excellence in clinical research.

Of utmost importance is our research infrastructure with a proven record of success, which is embedded in the elaborate system of prenatal clinics and obstetric services and complemented by our large and diverse population of over 6,600 deliveries per year, advanced support systems, strong division of Neonatology, outstanding follow-up programs and a patient population proven to be receptive to participation in research. The research staff is trained and certified in Good Clinical Practice, HIPPA, Blood Borne Pathogen Handling, and IATA Shipping Regulations. All staff is capable of collecting patient samples, cord blood and placental processing (including RNA, proteomics and DNA). Our research staff of over 25 individuals are trained and certified in each ongoing project. This maximizes efficiencies in recruitment and the performance of study procedures and also allows staff to share the responsibility of on-call coverage.

The Department of OB/GYN maintains a centralized administrative research office that manages pre- and post-award grant administration, and oversees roughly \$10 million in sponsored research funding annually. The Office analyzes, monitors, and evaluates the Department's research activities including all federal and non-federal sponsored awards and contracts. They

ensure the efficient, cost-effective administration and financial management and ensure compliance with internal and external policies and procedures.

